5.15 Blindedness Evaluation

At week 6 and either month 24 (V10), V10-equivalent visit due early study closure, an Unscheduled Visit due to study drug discontinuation, or a Discontinuation of In-person Followup Visit (whichever of the 4 visits comes first), the Site Investigator, Coordinator, and subject will complete a blindedness evaluation in which each is asked to give his/her independent impression of the subject's treatment assignment and the primary and secondary reasons for this opinion. Participants' responses will not be available to the site Investigator or Coordinator when they make their assessments.

5.16 Genetics

DNA samples will be sequenced using whole genome sequencing (WGS) supported by the NIH's Accelerating Medicines Partnership for Parkinson's Disease (AMP-

PD; https://www.nih.gov/research-training/accelerating-medicines-partnership-amp/parkinsons-disease) based on established methods (e.g, Allen *et al.* 2016), with variants scored under the AMP program

(e.g, http://www.type2diabetesgenetics.org/variantSearch/variantSearchWF; Butkiewicz et al. 2018). The following single nucleotide polymorphisms (SNPs) or repeat polymorphisms may be investigated amongst emerging genetic variants contributing to progression of PD across motor, non-motor and holistic domains (Iwaki et al. 2019), with simple additive, recessive, dominant, interactive, haplotypic, polygenic or other models to be determined based on current understanding of genetic risk determinants upon availability of WGS expected by early 2020. Genetic predictors of PD progression that may be specific for urate-targeting inosine treatment, and those that are more likely generalized will be considered:

- Potential predictors of PD progression, specific to urate/inosine intervention; e.g.:
 - o rs1109303 (INPP5K), stratifying for TT vs G carriers (Nazeri et al. 2015)
 - s6855911, rs7442295, rs16890979 (*SLC2A9*; encoding urate transporter gene *Glut9*), adjusting for and stratifying by a composite score of proportional to the # of their minor alleles) (Simon et al. 2014)
 - rs2231142 (*ABCG2* encoding urate transporter gene), stratifying for CC vs A carriers (Matsuo et al. 2015)
- Potential predictors of PD progression, generalized; e.g.:
 - o rs76904798 (near/5' to *LRRK2*) (Iwaki et al. 2019)
 - D4S3481 (*SNCA*-Rep1; complex repeat polymorphism upstream of *SNCA*) (Ritz et al. 2012)
 - o rs76763715 (GBA N370S; but MAF 0.007) (Davis et al. 2016)
 - rs9298897 and rs17710829, alone and in a modeled interaction (Latourelle et al. 2017)
 - rs2230288 (*GBA*), rs17649553 (*MAPT*), apolipoprotein E4 (*APOE4*), COMT val¹⁵⁸met (*COMT*) and BDNF val⁶⁶met (*BDNF*) alone and in additive model for cognitive progression outcomes (Iwaki et al. 2019; Caspell-Garcia et al. 2017).

5.17 Exploratory Assessments

Three brief, self-administered questionnaires will be included to explore whether readily ascertained historical factors modify or otherwise interact with inosine effects.

- **REM Sleep Behavior Disorder (RBD) Single-Question** Screen (RBD1Q)– A single "yes-no" question on dream-enactment behaviour will be asked at SC1, BL, and 3 mo, 12 mo, 24 mo, and 27 mo visits.
- **PD Risk Factors Questionnaire** A self-administered questionnaire assessing exposures and experiences linked to the risk of PD will be collected at BL. The questionnaire was developed by the PSG and derived from NINDS CDEs.
- **PD Expectancy Questionnaire** A self-administered questionnaire assessing expectations of study drug effect will be collected at BL.

• Smart4SURE assessments – A set of smartphone metrics of parkinsonian features adapted from the mPower app developed as a sub-study of SURE-PD3.

6. Statistical Methodology

6.1 General Considerations

6.1.1 Statistical Software

All statistical analyses will be performed using SAS (SAS Institute, NC, USA) or R (R Foundation for Statistical Computing, Vienna, Austria).

6.1.2 Summary Statistics

Data will be summarized with respect to disposition, demographics, pre-treatment characteristics, safety outcomes, tolerability, and efficacy outcomes. Summary statistics for continuous variables will include the number of subjects, the mean, median, standard deviation, and range. For categorical data, summaries will include counts and percentages.

6.1.3 Precision

Results will generally be reported to 3 significant figures. Percentages will generally be reported to 0.1 percentage points. P-values will be reported to two digits when greater than or equal to 0.095, to three digits when greater than or equal to 0.00095 and less than 0.095, and as <0.001 for all smaller values.

6.1.4 Administration

A test set of tables and figures specified in the SAP will be produced prior to breaking the blind using a dummy randomization schedule. The SAP will be finalized and must be approved by the Steering Committee prior to the final lock of the trial data and breaking of the blind.

6.2 Analysis Samples

The following analysis samples will be used for testing effectiveness, efficacy, safety, and tolerability endpoints:

- Intent-to-treat (ITT) Sample: Participants who are randomized, classified according to their randomized treatment assignment. Participants determined to have been ineligible prior to randomization, participants who never initiate study drug, and observations made after premature permanent discontinuation of study drug are included in this sample.
- As-treated (AT) Sample: Participants who are eligible, randomized, and take at least one dose of study drug. If a participant permanently discontinues study drug, observations made during period 1 will be censored following the first visit after study drug discontinuation. Separate analyses will classify participants in the AT sample either according to the actual treatment received or according to the average post-baseline serum urate concentration achieved. Participants randomized to inosine who report not taking inosine will be reclassified as placebo participants. Participants randomized to placebo who report taking inosine or whose serum urate during treatment averages 6.5 mg/dL or greater will be reclassified as inosine participants.

• Safety and Tolerability (ST) Sample: Participants who are randomized and take at least one dose of study drug, classified according to the actual treatment received. Participants determined to have been ineligible prior to randomization and observations made after premature permanent discontinuation of study drug are included in this sample.

The primary efficacy analyses will use the ITT sample to best estimate the expected effectiveness of urate-elevating oral inosine supplementation in clinical practice, recognizing that compliance in clinical use may differ from compliance in the clinical trial. Secondary analyses of efficacy outcomes will use the AT sample to best estimate efficacy of inosine supplementation as administered and serum urate elevation as achieved. Analyses of safety and tolerance will use the ST sample.

6.3 Baseline Comparison

While recognizing that any difference observed between treatment groups is axiomatically due to chance, nominal p-values will be calculated as a measure of the magnitude of difference for each baseline characteristic summarized using Fisher's exact tests for nominal variables, exact Cochran-Armitage trend tests for ordinal variables, and two-sample t-tests for approximately continuous variables.

6.4 Sample Size Review

Estimates of variance components and censoring and drop-out rates required for sample size calculation will be reviewed periodically using blinded data. No formal sample size re-estimation is proposed.

6.5 Interim Analysis

Interim analyses for efficacy or futility will be performed by the unblinded statistician using an information-based group-sequential design. Interim analyses will be performed after approximately 2000 and 5000 person-months of period 1 follow-up are completed, roughly one-third and threequarters of total anticipated period 1 follow-up. Non-binding early stopping for efficacy will be proposed if the active treatment group is superior to placebo for the primary efficacy outcome based on a one-sided p-value of 0.001 or less. Other criteria used in deciding whether to stop early for efficacy will include evaluation of safety and secondary efficacy outcomes. We propose stringent early stopping criteria for efficacy in order to ensure that evidence for efficacy is unambiguous if the study is stopped early. Non-binding early stopping for futility will be proposed based on a beta-spending rule quadratic in information time. If there were no benefit from treatment, then the trial would have a 51% probability of early stopping for futility based on this rule. As with the efficacy evaluation, the decision to stop early for futility will also include evaluation of feasibility, safety, and secondary efficacy outcomes. Because the efficacy and futility stopping rules are non-binding, we conservatively assume that each look is cumulative for alpha and ignore possible findings of futility when calculating the overall type I error.

6.6.3 Secondary Efficacy Endpoints

Continuous secondary efficacy endpoints will all be analyzed using the ITT and AT samples and the primary and secondary efficacy analysis described above. Variables that are strongly right-skewed will be log-transformed prior to analysis, and estimates will be back-transformed for reporting.

The binary indicator of orthostatic hypotension will be analyzed in an equivalent generalized mixed model treating the indicator variable as a Bernoulli random variable with logit link.

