- Wash-out (Period 2) of 90 ± 7 days, ending ~27 months after enrollment. Three monthly evaluations will be conducted after discontinuation of study drug at V10 (after 24 months of treatment), two by phone (TE1 and TE2 at months 25 and 26, respectively) and the final visit (SV) in person at month 27. The multiple visits will allow for serial assessments of the need for dopaminergic therapy during and after the reversal of any short-term effect of inosine or its withdrawal, as well as for any late adverse effects of the treatment or its withdrawal.

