3.8 Sample Size

urate. Early, largely untreated PD subjects with a serum urate of <5.9 mg/dL at baseline from DATATOP (n=155; double-placebo only), PRECEPT (n=446) and SURE-PD (n=25; placebo only) were followed for up to two years. The overall UPDRS rate was obtained by weighting each estimate by the inverse of its standard error.

Power for the primary outcome of rate of change in MDS-UPDRS I-III total score is based on a random slopes model with shared baseline. The model will include fixed effects of time, treatment x time, sex, sex x time, an indicator of baseline MAO-B inhibitor use, and baseline MAO-B inhibitor use x time and random site- and subject-specific intercepts and slopes, each with unstructured covariance. MDS-UPDRS assessments completed after a subject has initiated dopaminergic therapy will be censored.

Based on applying the same primary analysis model to data from SURE-PD, the following variance components were estimated for UPDRS I-III total scores: site-level variance (intercept = 9.75, slope = 0.0123 / month, covariance = -0.346), subject-level variance (intercept = 77.4, slope = 0.230 / month, covariance =2.87), and residual variance = 13.9. We assume that 70% of subjects will initiate dopaminergic therapy based on experience in SURE-PD plus up to 8% additional lost to follow-up prior to initiating dopaminergic therapy. With the planned schedule for MDS-UPDRS assessments (screening, baseline, 3 weeks, 6 weeks, 12 weeks, and then

quarterly through 24 months), the variance and censoring estimates above imply an effective standard deviation for UPDRS I-III total score slopes of 0.587 units / month or 0.758 units / month on the scale of MDS-UPDRS I-III total scores.¹²

Given a standard deviation of 0.76 units / month, a final two-sided test at alpha = 0.046 allowing conservatively for two interim analyses at alpha = 0.001 each, the study would have 80% power with n = 270 subjects randomized 1:1 to placebo or urate elevation if the true effect of treatment were to reduce the rate of increase in MDS-UPDRS I-III total score by 6.3 points over 2 years.

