3.9 Power for Secondary Outcomes

The trial will have an 80% probability of observing at least one instance of any class of adverse event expected to occur in at least 1.2% of individuals receiving inosine. The trial will have 80% power to detect increased risk of any class of adverse event among subjects receiving inosine if the true risk is two-fold higher and the expected proportion among placebo subjects is at least 14% or if the true risk if four-fold higher and the expected proportion among placebo subjects is at least 3.4%. The trial has 80% probability of declaring serum urate elevation tolerable if the true proportion tolerant under the definition given in Sec. 3.4 at 12 weeks, 12 months, and 24 months is at least 62%.

The estimated SE for symptomatic effects on UPDRS I-III total scores during wash-in between the moderate elevation and placebo arms in the SURE-PD trial was 0.53 units / month. With n = 25 subjects per treatment group in SURE-PD, the expected SE for estimating symptomatic effects in this trial will be roughly sqrt (25/135) * 0.53 = 0.23 units / month. With that SE, the trial would have 80% power to detect symptomatic effects on the order of a difference in slopes during wash-in or wash-out of 0.65 units/month.

The Kaplan-Meier product-limit estimate from the SURE-PD trial of the proportion of placebo subjects requiring dopaminergic therapy by 24 months was 62%. Assuming constant hazard at the same rate among placebo subjects in this trial during period 1 (0 to 24 months) and 8% loss to follow-up prior to determining need for dopaminergic therapy, the trial will have 80% power to detect a hazard ratio of 0.62. Extrapolating to 27 months, we expect a total of 67% of placebo arm subjects to have disability warranting dopaminergic therapy at the end of period 2 (24 to 27 months). The study would have 80% power to detect a difference in the proportion of subjects with disability warranting dopaminergic therapy if 50% or fewer of active arm subjects have progressed by the end of the trial.

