5.9 Initiation of Dopaminergic Therapy

For the purposes of this trial, the date at which a participant initiates dopaminergic therapy will be calculated as the first day that the participant either (a) initiates use of one of the following medications as labeled in the WHO Drug Dictionary: amantadine, pramipexole, ropinirole, rotigotine, sinemet, trihexyphenidyl, benztropine, rasagiline, selegiline, safinamide, or levodopa at a LEDD greater than 2 mg/day, or (b) increases the LEDD of one of the following medications over the dosage taken at baseline by more than 2 mg/day: rasagiline, selegiline, safinamide.

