- 6. At each time any oral levodopa is taken per day, if tolcapone (e.g., Tasmar) is taken at the same time, then multiply the total levodopa dosage at that time (quantity 4) by 0.50
- 7. Calculated the COMT-adjusted total daily levodopa equivalent dosage associated with oral levodopa as the sum over all time points of quantities 4 through 6
- 8. If enteral levodopa is taken without any COMT inhibitor, then multiply the total enteral levodopa (e.g., Duopa) daily dosage (mg) by 1.11
- 9. If enteral levodopa is taken with entacapone but not tolcapone, then multiply the total daily enteral levodopa dosage (mg) by 1.48
- 10. If enteral levodopa is taken with tolcapone, then multiply the total daily enteral levodopa dosage (mg) by 1.67
- 11. If immediate release or modified release pramipexole (e.g., Mirapex) is taken, multiply the daily dosage (mg/day of the dihydrochloride monohydrate salt) by 100
- 12. If immediate release or extended release ropinirole (e.g., Requip, Requip XL) is taken, multiply the dosage (mg/day) by 20
- 13. If a rotigotine patch (e.g., Neupro) is used, multiply the dosage (mg/day) by 30
- 14. If oral selegiline (e.g., Eldepryl) is taken, multiply the dosage (mg/day) by 10
- 15. If sublingual selegiline (e.g., Zelapar) is taken, multiply the dosage (mg/day) by 80
- 16. If oral rasagiline (e.g., Azilect) is taken, multiply the dosage (mg/day) by 100
- 17. If oral safinamide (e.g., Xadago) is taken, multiply the dosage (mg/day) by 2
- 18. If oral amantadine (e.g., Symmetrel) is taken, multiply the dosage (mg/day) by 1
- 19. If an injection or infusion of apomorphine (e.g., Apokyn) is taken, multiply the dosage (mg/day) by 10
- 20. If oral trihexyphenidyl (e.g., Artane) is taken, multiply the dosage (mg/day) by 25
- 21. If oral benztropine (e.g., Cogentin) is taken, multiply the dosage (mg/day) by 50
- 22. Calculate total LEDD as the sum of quantities 7 through 21.

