6.6.10 Multiplicity Adjustments

With two interim efficacy analyses each testing for benefit of serum urate elevation at a onesided p < 0.001, the final primary analysis tested using a two-sided p < 0.046 ensures that the overall type I error rate is under 5%. Results from analysis of secondary efficacy endpoints and subgroup analyses will report nominal, comparison-wise p-values, recognizing that the totality of results will be evaluated in judging the potential efficacy of serum urate elevation.

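### SAP 6.6.3 conflicts with SAP 3.2 on dopaminergic censoring and LEDD adjustment, so LEDD and MDS-UPDRS Part IV lack a workable treatment comparison and 12 Neuro-QOL modules and DAT lack a stated follow-up window

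*SAP*

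**What the plan says.** - **The general rule.** SAP 6.6.3: "Continuous secondary efficacy endpoints will all be analyzed using the ITT and AT samples and the primary and secondary efficacy analysis described above". No exception is listed. The same section log-transforms any strongly right-skewed variable.
- **What it points to.** SAP 6.6.1 fits a shared-baseline random-slopes model to period 1 and drops observations after dopaminergic initiation. The alternatives in 6.6.2 keep that censoring, except the LEDD-adjusted version, which restores later data and adds time-dependent LEDD as a covariate.
- **The narrower statement.** SAP 3.2 lists LEDD and DAT among the outcomes, then gives the choice between excluding later data and adjusting for LEDD only for symptom measures taken from the MDS-UPDRS.
- **The protocol.** Section 10.5.6 applied the primary model to *most* secondary measures. SAP 1 makes the SAP prevail on analysis.
- **Endpoints and timing.** SAP 4.3 lists LEDD, Part IV, DAT and 13 Neuro-QOL modules as secondary efficacy endpoints. Part IV is collected only after symptomatic therapy has begun (SAP 5.1). Neuro-QOL modules other than Depression are given at SC2 and SV only (5.8). DAT is measured at DS1 and DS2, with DS2 one to two months after V10 (5.12). SV and DS2 fall in the wash-out; protocol 3.3 says: "Three monthly evaluations will be conducted after discontinuation of study drug at V10".
- **Error control.** SAP 6.6.10: "Results from analysis of secondary efficacy endpoints and subgroup analyses will report nominal, comparison-wise p-values".

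**The concern.** The 6.6.1 and 6.6.2 analyses were built for a symptom score that dopaminergic therapy masks. Carried over to *all* continuous secondary endpoints, they meet some for which they cannot work: LEDD, which is itself the therapy; Part IV, which exists only after therapy starts; and measures with no period-1 follow-up value.

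LEDD is the only planned endpoint for how much therapy is used. The time-to-disability test (SAP 6.6.4) and the combined rank test (6.6.5) address when therapy is needed. If the rule is followed literally, the LEDD result is empty. If it is not, the replacement is chosen by whoever programs the tables.

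**Working it through.** **1. What the plan's own power figure implies.** SAP 3.9 gives 10.3 points as the detectable 2-year difference for PDQ-39, with SD 30 and 80% power. Alpha is not stated for this endpoint; 0.05 two-sided is assumed.

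- With 135 per arm: (1.960 + 0.842) × 30 × √(2/135) = 10.23. At alpha 0.046 it is 10.36. The plan's figure reproduces.
- With 70% initiating and 8% more lost (SAP 3.8), 22% remain: 135 × 0.22 ≈ 30 per arm. Then 2.802 × 30 × √(2/30) = 21.7.

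So 10.3 was computed without dopaminergic censoring. It also ignores loss to follow-up, so it is a pointer to the authors' intent, not proof.

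**2. Count of continuous secondary endpoints (SAP 4.3).** MDS-UPDRS 6 + DAT 1 + Neuro-QOL 13 + MoCA 1 + PDQ-39 1 + Schwab and England 1 + orthostatic changes 3 + LEDD 1 = 27.

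**3. LEDD under 6.6.3 as written.**

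- *Censored.* Initiation is itself defined by LEDD-generating drugs (SAP 5.9), so what remains is essentially the baseline value. The exceptions are small. Censoring for a baseline MAO-B inhibitor starts only when a participant "increases the LEDD of one of the following medications over the dosage taken at baseline by more than 2 mg/day", so smaller rises stay in, as do reductions. Drugs that count towards LEDD but are not in the 5.9 list also stay in, such as apomorphine (SAP 5.14: "If an injection or infusion of apomorphine (e.g., Apokyn) is taken").
- *LEDD-adjusted.* The model is LEDD = intercept + time + treatment × time + … + γ·LEDD. It is solved exactly by γ = 1 with every other coefficient 0. A least-squares fit to simulated data confirmed this: treatment × time coefficient and residual SD both zero to machine precision.
- *Log rule.* Untreated participants not on an MAO-B inhibitor have LEDD = 0, so the logarithm is undefined. This applies under 3.2 as well.

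**4. Part IV.** Under censoring, essentially no records remain. Under LEDD adjustment there are up to 9 period-1 visits per initiator (V02 to V10). There is no baseline value, no rule assigns a score to untreated participants, and the arms consist of people selected by an event after randomisation. Part IV is itself an MDS-UPDRS score, so 3.2 gives the same result.

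**5. Twelve Neuro-QOL modules and DAT (12 + 1 = 13 endpoints).** Under the 6.6.1 period-1 window, no follow-up value enters. The as-treated rule is also written for period 1 (SAP 6.2: "observations made during period 1 will be censored following the first visit after study drug discontinuation") and does not say how SV or DS2 is treated. If period 2 is admitted, the repeated-measures model in 6.6.2 can be fitted. The random-slopes model is a poor choice: two occasions give three distinct variance and covariance elements, against four participant-level parameters.

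If period 2 is admitted but censoring is kept, the SV counts below follow. They treat need for therapy as initiation and assume full follow-up. The active-arm inputs (50% progressed, hazard ratio 0.62) are detectable-effect scenarios in SAP 3.9, not expectations.

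- From SAP 3.9 ("we expect a total of 67% of placebo arm subjects to have disability warranting dopaminergic therapy at the end of period 2"; active 50%; 8% lost): placebo 135 × 0.33 × 0.92 = 41; active 135 × 0.50 × 0.92 = 62. Subtracting the 8% instead: 135 × 0.25 = 34 and 135 × 0.42 = 57.
- From SAP 3.8 ("We assume that 70% of subjects will initiate dopaminergic therapy based on experience in SURE-PD"), taking 70% as the 24-month placebo rate, constant hazard and hazard ratio 0.62: placebo survival 0.30^(27/24) = 0.2581, active 0.30^(0.62 × 27/24) = 0.4318. Counts 135 × 0.2581 × 0.92 = 32 and 135 × 0.4318 × 0.92 = 54; subtracting the 8%, 24 and 47.
- Without censoring: 135 × 0.92 = 124 per arm.

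For DS2, from 62% at 24 months (SAP 3.9), the share of placebo participants past initiation is 1 − 0.38^(25/24) = 63.5% to 1 − 0.38^(26/24) = 64.9%. The substudy is opt-in, so no count is given.

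**The case against.** The best reply is that SAP 3.2 already answers the LEDD question. It is the specific statement, it confines the pair to MDS-UPDRS measures, and SAP 3.6 points the same way by ascribing the lack of wash-out data to censored MDS-UPDRS trajectories and contrasting measures that can be evaluated at the end of both periods. The PDQ-39 power figure fits this. On that view 6.6.3 carries over samples and model families only. For DAT, protocol 10.5.11 gives a two-visit shared-baseline model with no dopaminergic censoring, and SAP 1 leaves ancillary analyses to ancillary SAPs where the SAP does not cover them. For Neuro-QOL, only a window is missing.

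Much of this stands. A reader might infer that the plan leaves all four groups of endpoints without any analysis, or that LEDD is definitely to be censored or adjusted for itself. The documents do not support that: the LEDD problem is a conflict between two sections of the SAP, DAT needs a cross-reference, and Neuro-QOL needs a stated window.

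The reply does not dispose of the point. Section 3.2 does not say that other measures are exempt, 6.6.3 says *all*, and SAP 1 ranks the SAP over the protocol but not one SAP section over another. Even under 3.2, Part IV has no valid comparison, the log rule fails for LEDD, and no period-2 window is given for Neuro-QOL. SAP 4.3 lists DAT as an endpoint of the main trial, where 6.6.3 governs it.

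**Conclusion.** The point holds as a conflict within the SAP plus three gaps. Of 27 continuous secondary endpoints, two (LEDD and Part IV) need a rule of their own: LEDD because the literal rule yields nothing and the log rule fails on any reading, Part IV because no reading gives a valid between-arm comparison. Thirteen more need a window (12 Neuro-QOL modules) or a cross-reference (DAT).

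Keeping the censoring while admitting period 2 would leave about 24 to 41 placebo and 47 to 62 active SV values instead of about 124 per arm. Those counts rest on constant hazard where extrapolated, on detectable-effect scenarios for the active arm, and on full follow-up. SAP 4.6 and 4.8 record an early closeout, which would lower all of them.

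The primary analysis and its type I error are untouched, and secondary p-values are nominal. This should be fixed before database lock because the correction is short and the choice should not be made after unblinding.

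**What to change.** Amend SAP 6.6.3 as follows.

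- **Scope.** Apply dopaminergic censoring and LEDD adjustment only to MDS-UPDRS Parts I, II, III, ambulation and IB+II, in line with 3.2.
- **LEDD.** Use all period-1 visits, with no censoring, no LEDD covariate and no log transformation, in the 6.6.2 shared-baseline repeated-measures model. Support this with a rank test at 24 months or the V10-equivalent visit, because many values are zero.
- **Part IV.** Report descriptively among initiators.
- **Neuro-QOL modules other than Depression.** State that the 6.6.2 repeated-measures model runs from SC2 to SV without dopaminergic censoring.
- **DAT.** Cross-refer to protocol 10.5.11.

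**Cost.** A few lines of text and some programming; no new data. Part IV loses its between-arm test. The Neuro-QOL result describes status regardless of dopaminergic therapy, about three months off study drug. Seven other endpoints (27 − 6 − 1 − 12 − 1: MoCA, PDQ-39, Schwab and England, Neuro-QOL Depression and three orthostatic changes) would also be analysed regardless of dopaminergic therapy. That is a different estimand from the primary, but it is what 3.2 and the PDQ-39 power figure already imply. The unstructured covariance may be hard to fit for LEDD while most early values are zero, which is a further reason for the rank test.
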